This study will be conducted in accordance with International Conference on Harmonisation (ICH) Guideline for Good Clinical Practice (ICH E6[R2]), applicable United States Code of Federal Regulations (CFR), Title 21, as well as all applicable local, state, and federal regulations and guidelines regarding the conduct of clinical studies. In addition, this study will be conducted in accordance with the ethical principles included in the World Medical Assembly (WMA) Declaration of Helsinki, *Ethical Principles for Medical Research Involving Human Subjects* adopted by the 18th WMA General Assembly, Helsinki, Finland, June 1964, and amended most recently by the 64th WMA General Assembly, Fortaleza, Brazil, October 2013.

Throughout this protocol, the term "Clinical Investigator" or "Investigator" will be defined, in accordance with 21 CFR 54, as any listed or identified principal investigator (PI) or subinvestigator who is directly involved in study dosing or evaluation of research subjects. PIs or subinvestigators must be listed on Form FDA 1572 and documented as appropriate on the delegation of authority signature log. The PI will assure that no deviation from or changes to the protocol will take place without prior agreement from the Investigational New Drug (IND) sponsor and documented approval from the Institutional Review Board (IRB)/Independent Ethics Committee (IEC), except where necessary to eliminate an immediate hazard(s) to the trial participants. All personnel involved in the conduct of this study will have completed Human Subjects Protection and ICH GCP Training.

The protocol, informed consent form(s), recruitment materials, and all participant materials will be submitted to the IRB/IEC for review and approval. Approval of both the protocol and the consent form must be obtained before any participant is enrolled. All changes to the consent form will be IRB/IEC approved; a determination will be made regarding whether a new consent needs to be obtained from participants who provided consent using a previously approved consent form.

PROTOCOL AGREEMENT

1.1 Summary

Protocol Number 02-CL-2001a

Title: A Multicenter, Single-Treatment Study to Assess the Safety and

Tolerability of Lyophilized Lucinactant in Adults with COVID-19

Associated Acute Lung Injury

Phase: 2a

US IND Number: 149624

Sponsor: Windtree Therapeutics, Inc. (Windtree), Warrington, PA, USA

ClinicalTrials.gov No.: NCT04389671

Committees: DMC

Study Drug: Lyophilized lucinactant reconstituted with sterile water for injection

and administered at a dose of 160 ml (~80 mg total phospholipids

(TPL)/kg lean body weight), delivered as a liquid.

Rationale: The coronavirus that was first detected in China in 2019 and which

has been detected in over 190 countries on every continent, has infected over 150 million people worldwide (including approximately 3 million deaths), including approximately 35 million in the United States (including over 600,000 deaths). The virus has been named "SARS-CoV-2" and the disease it causes has been named

"coronavirus disease 2019" (abbreviated "COVID-19").

Coronaviruses are a large family of viruses that are common in people and many different species of animals, including camels, cattle, cats, and bats. Rarely, animal coronaviruses can infect people and then spread between people such as with MERS-CoV, SARS-CoV, and

now with this new virus. The SARS-CoV-2 virus is a betacoronavirus, like MERS-CoV and SARS-CoV. All three of these viruses have their origins in bats. The viral sequences from U.S. patients are similar to the one that China initially posted, suggesting a likely single, recent emergence of this virus from an animal reservoir.

Surfactants, specifically lucinactant, have been studied in acute hypoxemic respiratory failure and in acute lung injury. It is hypothesized that lucinactant may improve the respiratory status of patients suffering from COVID-19.

Lucinactant is a synthetic surfactant that is approved by the US FDA (NDA 021746) for the prevention of respiratory distress syndrome (RDS) in premature infants at high risk for RDS. It has been safely administered to over 1000 children and adults. Preliminary data from animal and human adult studies indicate that lucinactant could benefit those with acute respiratory distress syndrome (ARDS) in the context of COVID-19 infection, improving oxygenation and lessening lung damage. When given after intubation, lucinactant could potentially decrease the duration of ventilation or extracorporeal membrane oxygenation (ECMO).

ARDS, as a consequence of COVID-19 infection, seems to have a significant negative impact on surfactant related lung function. SARS-CoV-2 uses the SARS-coronavirus receptor, angiotensin-converting enzyme 2 (ACE2) for entry into the host cells. ACE2 is a surface molecule on alveolar Type 2 cells of lung. Type 2 cells are the source of surfactant in the lung and if they are damaged surfactant production is impaired, resulting in decreased lung compliance. This appears to occur early in the course of COVID-19 lung injury. This increases the likelihood of the need for mechanical ventilation, which may further damage the lungs. Recent publications suggest that lung fibrosis and severe interstitial changes occur in COVID-19 patients who developed ARDS.

[figure not shown]
In addition to the direct lung injury caused by COVID-19, there is a subsequent damage to the lung through triggering and activation of the inflammatory cascade, similar to that involved in the development of

bronchopulmonary dysplasia (BPD). There is data supporting benefit of lucinactant to decrease the incidence and severity of BPD, supporting the rationale for use of exogenous surfactant in the treatment of pulmonary disease caused by COVID-19.

Lucinactant significantly reduced mortality in a related pre-clinical model of H5N1 in ferrets infected with highly pathogenic avian

influenza. Results showed that surfactant treatment significantly improved survival, as well as viraland inflammation-related lung damage.

Clinical evidence in patients with acute lung injury (ALI) showed potentially beneficial results in children on mechanical ventilation due

to severe respiratory syncytial virus (RSV) infection, including pneumonia. Many studies in clinical ARDS have substantiated that damage to surfactant and inadequate quantities of functioning surfactant contribute to the pathophysiology of ARDS. Several studies in adult ARDS have established that lucinactant can be safely administered to critically ill patients and potentially replenish the surfactant pool.

In many animal models, surfactant replacement therapy of pneumonia has been studied showing decreased intrapulmonary bacterial proliferation, decreased bacterial growth, and improved pulmonary function with increased pulmonary compliance. Clinical studies of surfactant in subjects with pneumonia have shown improvements in oxygenation and mean airway pressure, with one study showing a reduced need for ECMO. A series of *in vitro* studies have shown that a synthetic surfactant containing KL4 peptide tends to be more resistant to inhibition by four serum components (fibrinogen, C-

reactive protein, platelet activating factor, lyso-phospatidylcholine) known to inhibit surfactant activity when compared with an animal derived surfactant.

A study on recombinant surfactant protein C-based surfactant, indicated that among patients with ARDS caused by a direct lung injury, those who received surfactant tended to have a higher survival rate than those who received standard therapy. In fact, an oxygenation benefit was found across the entire population of patients who received surfactant.

Lucinactant has an extensive safety profile and has been safely administered to over 1000 subjects in different patient populations (adults, infants, toddlers) for different indications (eg, respiratory distress syndrome of the newborn (RDS), acute hypoxemic respiratory failure (AHRF), ARDS). In almost all cases, there were no safety signals of concern with rates of adverse events (AEs) being similar to control (placebo and active). An increase in AEs was noted in one study when using bronchoalveolar lavage to administer SURFAXIN; however, bronchoalveolar lavage is no longer used and lyophilized lucinactant has a much lower viscosity then SURFAXIN, which also should minimize any temporary airway obstruction.

It is hypothesized that lucinactant may improve the respiratory status of patients suffering from COVID-19.

Study Description:

This is a multicenter, single-treatment study. Subjects will consist of adults with COVID-19 associated acute lung injury who are being cared for in a critical care environment.

See Section 1.2, Schedule of Activities (SOA).

Study Objective:

To evaluate the safety and preliminary efficacy of lyophilized lucinactant, as assessed by oxygenation index (OI) through 12 hours post initiation of dosing and other physiological and outcome measurements through 24 hours or through Day 30.

Endpoints:

Primary Endpoints:

- Safety and Tolerability of reconstituted lyophilized lucinactant given as a bolus to patients with COVID-19.
- Change from baseline in OI at 12 hours post initiation of dosing. OI is defined as P_{aw}×FiO₂×100/PaO₂.

Secondary Efficacy Variables:

- Change from baseline through 24 hours post dosing initiation:
 - \circ FiO_{2:}
 - o PaO₂;
 - o SpO₂;
 - o OI;
 - o PaCO₂;
 - o ETCO₂;
 - P/F and or S/F ratios, defined as PaO₂ or SpO₂ divided by FiO₂;
 - Plateau pressure and peak inspiratory pressure (PIP) measured on the ventilator;
 - Ventilation Index (VI). VI is defined as $[RR \times (PIP PEEP) \times PaCO_2]/1000$;
 - o Lung compliance;
 - o Pressure-volume loops if ventilator technology permits.
- Through 30 days:
 - o Daily lung compliance (static) on ventilator;
 - Ventilator-free days;
 - o Days in the intensive care unit (ICU);
 - Days in the hospital;
 - o Incidence of all-cause mortality;
 - o Organ failure free days.

Safety Variables:

- All-cause mortality;
- Peri-dosing adverse events (desaturation, bradycardia, ET reflux, hypotension)
- AEs and serious AEs (SAEs). SAEs that are ongoing at Day 30 will be followed for an additional 30 days;
- Air leaks as AEs of special interest;
- Assessments of vital signs.

Study Population:

The study population will be comprised of adults 18-75 (inclusive) who are positive for SARS-CoV-2, are exhibiting symptoms of severe COVID-19 infection, who are intubated and are receiving mechanical ventilation in a critical care environment.

The objective of the pilot safety study is to evaluate the safety and feasibility of lucinactant administration in COVID-19 patients. A small number of patients should be sufficient to provide evidence that liquid lucinactant can be safely delivered as an intratracheal bolus. A total of up to 30 study subjects will be enrolled (see "Treatment Group" section).

Description of Sites:

Approximately 15 study sites in the United States and Argentina.

Description of Study Intervention:

Reconstituted lyophilized lucinactant will be given at a dose of 160 ml (30 mg TPL/ml), delivered as a liquid in the trachea through the endotracheal tube. Lyophilized lucinactant has the following four active ingredients:

- sinapultide (a synthetic peptide), consisting of amino acid residues lysine (K) and leucine (L), according to the sequence KLLLKLLLKLLLKLLLKKLLLK (KL₄);
- dipalmitoyl-phosphatidylcholine (DPPC);
- palmitoyloleoyl-phosphatidylglycerol, sodium salt (POPG, Na); and
- palmitic acid (PA).

Inclusion Criteria:

Each subject must meet all inclusion criteria to be enrolled in this study:

- 1. Signed and dated ICF (electronically or in ink) by the subject or legally authorized representative;
- 2. Age 18-75 (inclusive);
- 3. Assay positive for SARS-CoV-2 virus, preferably by polymerase chain reaction (PCR);
- 4. Endotracheal intubation and MV within 7 days of initial intubation;
- 5. In-dwelling arterial line;
- 6. P/F ratio < 300;
- 7. Mean blood pressure ≥ 65 mmHg, immediately before enrollment;
- 8. Bilateral infiltrates seen on frontal chest radiograph.

Exclusion Criteria:

Subjects meeting any exclusion criteria must not be enrolled in this study:

- 1. Life expectancy < 48 hours or do not resuscitate orders;
- 2. Severe lung disease (home O_2 , $FEV_1 < 2$ liters) not likely to respond to therapy or profound hypoxemia (ie, $OI \ge 25$ or P/F < 100);
- 3. Severe renal impairment (creatinine clearance < 30 mL/min);
- 4. Within the last 6 months has received, or is currently receiving, immunosuppression therapy (azathioprine, cyclophosphamide or methotrexate) or any transplant recipient;
- 5. Clinically significant cardiac disease that adversely effects cardiopulmonary function:
 - a. Acute coronary syndromes or active ischemic heart disease (as assessed by the PI using troponin and ECG)
 - b. Cardiac ejection fraction < 40% (if known);
 - c. Need for multiple-dose vasopressors to support blood pressure (single dose vasopressors, such as Levophed™ ≤ 0.1 mcg/kg/min are allowed);
 - d. Cardiogenic pulmonary edema as the etiology of the current respiratory distress;
 - e. Evidence of myocarditis or pericarditis;
- 6. Neuromuscular disease;
- 7. Neutropenia (ANC < 1000);

- 8. Active malignancy that impacts treatment decisions or life expectancy related to this trial;
- 9. Suspected concomitant bacterial or other viral lung infection. Bacterial infection defined as WBC > 15k and positive blood/ urine/sputum culture results within 72 hours.

Treatment Group:

Up to 30 enrolled subjects will be administered an investigational drug product, reconstituted lyophilized lucinactant. Prior to administration, lyophilized lucinactant will be reconstituted with sterile water for injection then delivered as a liquid into the trachea in quarter doses.

Lucinactant Lyophilized lucinactant 160 ml (~80 mg TPL/kg lean body weight of 30 mg/ml suspension)

Up to 3 repeat study treatments of the same dose volume may be given if criteria are met.

Enrollment should occur as soon as possible once it has been confirmed that the subject has met all inclusion criteria and has not met any exclusion criteria within 7 days of initial intubation. Treatment initiation is to begin within 6 hours of enrollment. If the subject does not tolerate one of the 40 ml quarter doses, the dosing for that dose may be terminated at that time. It is recommended that the other quarter doses remain 40 ml; however, a lower dose may be administered for the remaining aliquots at the Investigator's discretion.

Up to 3 retreatment doses are allowed no sooner than 6 hours apart (from completion of previous dose). Subjects are eligible for retreatments if they remain on MV, there is no evidence of pneumothorax, the P/F ratio is under 300 (or S/F ratio is under 315, if no arterial line is present), and there are no safety concerns that would prevent retreatment (in the opinion of the investigator). Retreatments are given at the discretion of the investigator.

Retreatment should be performed in the same manner as the initial treatment.

Early Discontinuation of Treatment:

The administration of study treatment may be discontinued at any time prior to the completion of dosing based on the clinical judgment of the PI. Reasons for discontinuation of study treatment include, but are not limited to the following:

- 1. An AE which places subject at risk occurs (eg, severe bradycardia, hypotension, cardiac arrest)
- 2. If, in the PI's best medical judgment, initiating or continuing the subject's exposure to study treatment is not in the best interest of the subject's safety.

Subjects whose treatment is discontinued based on the PI's judgment will continue in the study. Subjects whose treatment is discontinued based on the subject's request may continue in the study; however, if a subject withdraws consent, the subject will be withdrawn from the study and no further data collection will be done.

Study Duration:

Subject participation will be from enrollment to 30 days after enrollment unless they have an ongoing SAE (to be followed for an additional 30 days).

Overall, study enrollment will be completed in approximately 7 to 8 months, with the last subject last visit approximately 8 to 9 months from the time the first subject enrolled.

Statistical Analysis:

The statistical analysis will be based on all enrolled subjects.

For the efficacy analysis, populations of all enrolled subjects who received any treatment (modified intent-to-treat [mITT]) will be evaluated. For the safety analysis, all enrolled subjects who received any lucinactant (including partial doses) will be evaluated.

All efficacy and safety parameters will be evaluated using summary statistics. For continuous variables, n, mean, standard deviation, median, min, and max will be presented; for discrete variables, frequency and percent will be presented.

All deaths will be summarized using frequency and percent, overall and by type of death (respiratory or not respiratory) and included as part of the assessment of safety. Also, the deaths will be listed by subject and narratives for each death will be included.

1.2 Schedule of Activities (SOA)

		Primary Phase Through Day 30		
Measurement/Procedure	Screening	Treatment Period (Day 1)	Post-Treatment Period (Days 2-5)	Final Period (Days 6 to 30)
Informed consent	X			
Inclusion/exclusion Criteria	X			
Demographics	X			
Medical history	X			
Physical examination	X			
Enrollment		X		
Study treatment administration		X		
Vital signs	X	X	X^2	X
ABG (PaO ₂ , PaCO ₂ , pH)		X^1	X	X
FiO ₂ , SpO ₂ , P _{aw} , EtCO ₂		X^1	X	X
Ventilator parameters (rate, peak and plateau pressure, lung compliance)		X^2	X^2	
Respiratory support parameters	X	X	X	X
Pressure volume loops		X^3		
AEs/SAEs		X	X	X ⁵
Concomitant medications	X	X	X	X
Final Visit/Discharge				X^4

Note: Day 1 for all subjects is the day of enrollment.

Time 0 (study treatment), 1, 2, 4, 8, 12, 18, 24 hours after treatment

 $^{^{2}}$ $\,$ Recorded every 12 hours at 08:00 and 20:00 through Day 5.

³ Recorded every 2 hours through 24 hours.

⁴ Occurs at Day 30, withdrawal from the study, or death (whichever occurs first).

⁵ AEs ongoing at Day 30 will be followed for an additional 30 days or until stop date/time (whichever occurs first).

TABLE OF CONTENTS

TITLE PAGE	I
STATEMENT OF COMPLIANCE	3
PROTOCOL AGREEMENT	4
1 PROTOCOL 02-CL-2001A	5
1.1 Summary	5
1.2 Schedule of Activities (SOA)	14
TABLE OF CONTENTS	15
2 INTRODUCTION	19
2.1 Study Rationale	19
2.2 Background	19

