8.2.1 Gas Exchange Parameters and Arterial Blood Gases

Values for fraction of inspired oxygen (FiO₂), oxygenation from pulse oximetry (SpO₂), mean airway pressure (P_{aw}), end-tidal CO₂ (EtCO₂), and arterial blood gases (ABGs; PaO₂, PaCO₂, pH) will be recorded from just prior to dose administration and at 1 (\pm 0.25), 2 (\pm 0.25), 4 (\pm 0.5), 8 (\pm 0.5), 12 (\pm 1.0), 18 (\pm 1.0), and 24 (\pm 1.0) hours after dose administration, daily through Day 5, and at Day 30.

P/F and S/F ratios will be determined.

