8.2.3 Respiratory Support Parameters

Information on respiratory support parameters will be captured through Day 30 or discharge, whichever occurs first. For each intubation and change in respiratory support, the following must be documented:

• Date and time

- The type of respiratory support and mode
- The reason for each intubation and change of respiratory support

Lung compliance should be recorded every $12 (\pm 1.0)$ hours through Day 5. The plateau pressure and peak inspiratory pressure (PIP) will be measured every $12 (\pm 1.0)$ hours through Day 5. The ventilation index will be calculated.

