9.4.3 Analysis of the Secondary Endpoint(s)

9.4.3.1 Through 24 Hours Post Treatment

OI, FiO₂, PaO₂, SpO₂, PaCO₂, P/F and S/F ratios, change in plateau pressure and PIP measured on the ventilator, VI, and lung compliance will be summarized as change from baseline at each time point measured using mean, SD, median, minimum, and maximum.

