#### **4.3 Missing Data**

Missing values represent a potential source of bias in a clinical trial. Hence, every effort will be undertaken to fulfill all the requirements of the protocol concerning the collection and management of data; however, some missing data is inevitable. No imputation, including last observation carried forward, will be done for the any parameters; only available data will be considered. Any missing data or data anomalies will be communicated to the site(s) for clarification/resolution.

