### **5.4.3 Respiratory Support and Supplemental Oxygen**

The respiratory support includes mechanical ventilation and extracorporeal membrane oxygenation (ECMO). Information on respiratory support parameters will be captured from screening through Day 30 or discharge, whichever occurs first. For each intubation and change in respiratory support, date and time, the type of respiratory support and mode, the reason for each intubation and change of respiratory support will be documented.

Lung compliance should be recorded every 12 ( $\pm 1.0$ ) hours through Day 5. The plateau pressure and peak inspiratory pressure (PIP) will be measured every 12 ( $\pm 1.0$ ) hours through Day 5. The ventilation index will be calculated.

The number of subjects requiring respiratory support in the delivery room, including sustained inflation, will be summarized using frequency and percent.

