### **8.1 Baseline Definition**

Baseline is defined as the measurements at the start of study drug administration for subjects enrolled in the treatment.

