### **8.2 Windows for Visits**

Accurate clock times will be recorded for each timed event in military time (24-hour clock). Day 1 is the day of enrollment; Day 2 begins at midnight following enrollment; Day 3 is the 2nd day following randomization; Day 30 will be the 29th day after the day of randomization.

All assessments at pre-specified time points are to be conducted within the windows specified in the protocol. Summary tables will use the pre-specified time points, not the actual times, to summarize the data.

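### PIP, plateau pressure and ventilation index are change-from-baseline endpoints, but their ventilator readings follow the clock rather than dosing, and PEEP is in no collection list

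*Protocol*

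**What the plan says.** **Endpoints.** Protocol 1.1 and 3 and SAP 1.2.3 list change from baseline through 24 hours in plateau pressure, PIP and VI among the secondary efficacy endpoints. VI is [RR × (PIP − PEEP) × PaCO2]/1000. Protocol 9.4.3.1 says that "VI, and lung compliance will be summarized as change from baseline at each time point measured", together with plateau pressure and PIP; SAP 4.2.2 plans the same.

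**Baseline.** SAP 8.1: "Baseline is defined as the measurements at the start of study drug administration for subjects enrolled in the treatment".

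**Timing of gas exchange.** Under Protocol 8.2.1, FiO2, SpO2, mean airway pressure, end-tidal CO2 and blood gases "will be recorded from just prior to dose administration" and then at 1, 2, 4, 8, 12, 18 and 24 hours, each with a window.

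**Timing of ventilator readings.** In Protocol 1.2 and SAP 2.2.4 the ventilator row covers rate, peak and plateau pressure and compliance. It is marked for Day 1 and Days 2-5, with the footnote "Recorded every 12 hours at 08:00 and 20:00 through Day 5". Protocol 8.2.3 reads "The plateau pressure and peak inspiratory pressure (PIP) will be measured every" 12 (±1.0) hours through Day 5. SAP 5.4.3 gives the same interval and adds "The ventilation index will be calculated". Neither says from when the 12 hours are counted.

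**PEEP.** It appears in the VI formula and in the title of SAP Figure 2.7.3 (its change from baseline). It is not in the schedule, nor in Protocol 8.1.4, 8.1.5, 8.2.1 or 8.2.3, nor in SAP 5.4.3.

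**Data handling.** SAP 4.3: "No imputation, including last observation carried forward, will be done for the any parameters; only available data will be considered". SAP 8.2: "Summary tables will use the pre-specified time points, not the actual times, to summarize the data".

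**The concern.** This is a single-arm study, so change within the subject carries the efficacy information and depends on a sound baseline. For PIP, plateau pressure and ventilator rate, no passage guarantees a reading at the start of dosing or at a common time afterwards. Three things follow if the schedule is applied as written.

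- A subject with no usable pre-dose reading drops out of the change summaries, because nothing is imputed.
- For the others, the baseline may be hours old and the post-dose readings fall at scattered times. Clock readings have no nominal post-dose hour under which to be tabulated. The Day 1 08:00 reading is 6 hours before dosing for a subject dosed at 14:00, and 1 hour after it for one dosed at 07:00.
- VI combines PaCO2 taken at hours after dosing with rate and PIP taken at clock times, and needs a PEEP that neither document says will be recorded.

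The secondary endpoints are there to show that other measures agree with the oxygenation index. Blurred timing weakens that check, and a reading not taken at dosing cannot be recovered later.

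**Working it through.** The plan states no figure to reproduce. The check asks how often readings at 08:00 and 20:00 line up with dosing and with the blood gases. Inputs: the two clock times (Protocol 1.2); the ±1.0 hour tolerance (8.2.3); the blood gas windows (8.2.1); dosing within 6 hours of enrollment (6.1.2); up to 30 subjects (9.2). D is the clock time of dose start.

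**1. Counts of clock hours (no assumption about enrollment times)**
- Reading no more than 1 hour before dosing, taken exactly on the slot: D in 08:00-09:00 or 20:00-21:00, so 2 of 24. With ±1 hour on the reading, the slot may lie from D−2 to D+1. That is 3 hours in every 12, so up to 6 of 24.
- Reading at 12 ± 1 hours: D in 07:00-09:00 or 19:00-21:00, so 4 of 24. With tolerance the slot may lie from D+10 to D+14, so up to 8 of 24. Slots are 12 hours apart, so the 24 ± 1 hour count is the same.
- Examples: dosed at 14:00, readings fall at −6, +6 and +18 hours; dosed at 19:00, at −11, +1 and +13 hours.

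The tolerance figures are upper bounds, because the reading must happen to move in the helpful direction.

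**2. Matching PaCO2 for VI (assumption: D uniform over 24 hours)**

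Every subject has one slot in 0-12 hours and one in 12-24 hours after dosing.
- On the slot, 0-12 hours: the windows 1 ± 0.25, 2 ± 0.25, 4 ± 0.5, 8 ± 0.5 and the part of 12 ± 1 up to 12 cover 0.5 + 0.5 + 1 + 1 + 1 = 4 of 12 hours, or 33%.
- On the slot, 12-24 hours: 12-13, 17-19 and 23-24 cover 1 + 2 + 1 = 4 of 12 hours, or 33%.
- With ±1 hour, 0-12 hours: 0-5.5, 6.5-9.5 and 10-12 cover 10.5 of 12 hours, at most 87.5%.
- With ±1 hour, 12-24 hours: 12-14, 16-20 and 22-24 cover 8 of 12 hours, at most 66.7%.

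**3. Subjects with no same-day pre-dose reading (depends on enrollment times)**
- Enrollment uniform round the clock, dosing L hours later: the 08:00 reading on the enrollment day precedes dosing with probability (16 + L)/24. For L = 2 that is 18/24 = 75%, so 25% have none (7.5 of 30). For L = 6 it is 22/24 = 92%, so 8% have none (2.5 of 30).
- Enrollment between 08:00 and 18:00: none lacks a same-day reading, but it can be old. With L = 2, D runs from 10:00 to 20:00 and the 08:00 reading is 2 to 12 hours old, 7 on average.

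**4. Why PEEP matters to VI.** With assumed RR 25, PIP 30 and PaCO2 50, VI = 25 × (30 − PEEP) × 50/1000. This gives 31.25, 25.0 and 18.75 for PEEP of 5, 10 and 15.

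**The case against.** The best case on the other side has several parts.

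- **Screening may supply a value.** The schedule row for respiratory support parameters is marked at Screening and Day 1, and PIP and plateau pressure sit in Protocol 8.2.3 under that same title. This is a fair reading. But Protocol 8.1.4 names only start time, type and mode of support, and compliance. Screening may also be up to 24 hours before dosing (10.1.1.2). Compliance itself does have a screening value.
- **The pre-dose vital signs list is open.** Protocol 8.1.5 introduces it with *including*, and SAP Table 6.1.4 treats respiratory rate as a vital sign, so a rate may be taken. The list names mean airway pressure but none of PIP, plateau pressure, ventilator rate or PEEP.
- **Every 12 hours could mean from dosing.** Its ±1.0 hour equals the blood gas window at 12 and 24 hours, and on that reading those shortfalls disappear. The text does not say so, and both schedules fix clock times.
- **No passage promises a 12-hour PIP.** True; 12 hours is used here because it is the primary endpoint's time.
- **Pressure-volume loops every 2 hours might show PIP and PEEP.** They depend on the ventilator and are not named as a source.
- **Retreatment is allowed from 6 hours after the previous dose.** Readings at 12 and 24 hours after the first dose will therefore mix exposure states whatever the anchor. This limits what the fix can gain.

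A reader might go further and infer that most subjects would have no baseline, that VI cannot be computed, or that the sections contradict each other. The documents do not support this. Nothing bars a same-day reading taken before enrollment. The planned PEEP figure suggests that capture was intended, and the eCRF may provide for it. An unanchored 12-hour interval is also compatible with 08:00 and 20:00.

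**Conclusion.** The concern holds as a scheduling gap in named endpoints and should be fixed. PIP, plateau pressure and ventilator rate have no explicit dosing-tied reading although their change from baseline is to be reported, and PEEP is in no collection list in the protocol or SAP.

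The clock-hour counts (2, up to 6, of 24; 4, up to 8, of 24) need only that the 08:00/20:00 footnote is followed. The VI matching shares (33% in each half, at most 87.5% and 66.7%) also assume uniform dose times. The number without a same-day pre-dose reading is the least certain: zero with daytime enrollment, and about 8-25% with round-the-clock enrollment and a 2-6 hour lag. A higher share would need almost no delay between enrollment and dosing. That is unrealistic, because enrollment is defined by the request to prepare the drug, and 160 ml at 10 ml per vial means reconstituting 16 vials.

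The damage is limited. The summaries are descriptive and secondary, and n is reported, so losses would show. The primary oxygenation index endpoint is unaffected: all its components are scheduled just before dosing and at 12 hours.

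**What to change.** - In Protocol 1.2 and 8.2.3 and SAP 2.2.4 and 5.4.3, record rate, PIP, plateau pressure, PEEP and compliance at Time 0 (just before dosing) and with the 12- and 24-hour blood gases, using the Protocol 8.2.1 windows, then every 12 hours through Day 5. State the same anchor and window in all four places.
- In SAP 8.1, name the Time 0 reading as baseline for these variables, and say that VI is computed from ventilator values taken with the same blood gas as its PaCO2.
- Check whether the eCRF already has a PEEP field; add one if not.

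The cost is an amendment with IRB/IEC approval at about 15 sites in two countries, a few eCRF fields, and three bedside ventilator readouts at times when blood gases are already drawn. No new procedure is needed and treatment does not change.
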